2. INTRODUCTION

This statistical analysis plan describes the statistical analysis plan for the drug use investigation of Anametro I.V. Infusion 500 mg (hereinafter referred to as Anametro). In this plan, sentences cited from the Protocol are shown in *Italics*.

2.1. Study Design

This investigation is a prospective study with a central registration system in patients who have not used metronidazole (injection) in the past and have been administered this drug for treatment of anaerobic infection, infectious enterocolitis, or amebic dysentery. The observation period shall start on the day the treatment with this drug begins and end on the day the treatment is completed; however, it shall be cut off at Week 8 after the initiation of treatment (Day 56 counting from Day 1 as the day the treatment begins) if the treatment is prolonged. A sample size of 100 patients was selected based on the following consideration.

<Rationale for the Sample Size Determination>

The target sample size was set to be 100 patients, which should enable to detect, at 95% probability, an adverse reaction of which the true incidence rate is 3% in reference to adverse reaction of the least incidence in a clinical study of this drug (Study A6831005). This sample size should enable to confirm whether the types and incidence of adverse reaction related to this drug used for diseases other than intra-abdominal infection, and pelvic

inflammatory disease and other related diseases that were targeted in the clinical study would be similar to those occurred in Study A6831005.

2.2. Study Objectives

This Study will be conducted to investigate the safety and effectiveness of Anaemetro I.V. Infusion 500 mg in daily clinical practice. Additionally, it is intended to assess the following:

- *Adverse reactions unexpected from precautions, and*
- *Occurrence of adverse reactions under actual clinical settings*

3. INTERIM AND FINAL ANALYSIS

In this Study, interim analyses for periodic safety update report will be performed periodically. At the time of interim analyses, only the analyses of items necessary for periodic safety update report among the statistical analyses specified in this plan will be performed. In addition, the final analysis for the application for reexamination will be performed. At the time of the final analysis, all analyses specified in this plan will be performed.

4. HYPOTHESES AND DECISION RULES

4.1. Statistical Hypotheses

Because this Study is not a confirmatory investigation, the tests are considered as exploratory tests.

4.2. Statistical Decision Rules

Not applicable.

5. ANALYSIS SETS

5.1. Safety Analysis Set

The safety analysis set is the full analysis set that is as close as possible to all Anaemetro-treated patients. Specifically, the safety analysis set includes all registered or reported patients excluding any patients who meet any of the following criteria:

- a. The case report form could not be collected at all (description in the report, “case report form not collected”)
- b. There was a violation or deficiency in the contract (description in the report, “contract violation/deficiency”)
- c. There was a violation of registration (description in the report, “registration violation”)

- d. Administration of the drug under investigation is not reported at all (description in the report, “no administration information”)
- e. Information on adverse events is not reported at all - no visits after the first prescription day (description in the report “no adverse event information - no visits”)
- f. Information on adverse events is not reported at all - there is a visit after the first prescription day but no description of safety information (description in the report, “no adverse event information - no description”)

Details for each criterion should follow the “Guidance for Criteria for Inclusion in Analysis Sets and Handling of Data in Drug Use Investigations”.

5.2. Effectiveness Analysis Sets

There are two effectiveness analysis sets, the clinical response analysis set and the microbiological response analysis set.

5.2.1. Clinical Response Analysis Set

The clinical response analysis set consists of the patients in the safety analysis set excluding any patients who meet any of the following criteria:

- g. No information of clinical response (description in the report, “no clinical response information”)
- h. Non-target disease of the study (description in the report, “Non-target disease of the study”)

That is, “others” is checked with no other information in the CRF item that asks the disease (diagnosis) that required the use of Anaemetro.

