7.2.1. Inclusion criteria

Patients who have not used metronidazole (injection) in the past, and have been administered this drug for treatment of anaerobic infection, infectious enterocolitis, or amebic dysentery. Patients who have used metronidazole (oral agent and vaginal tablet) in the past are eligible, and should not be excluded from this study.

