7.6.2. Patient registration

7.6.2.1. Procedure of patient registration

(1) Registration

The following registration items should be completed in the registration forms for patients with anaerobic infection, infectious enterocolitis, or amebic dysentery who are given Anaemetron I.V. Infusion 500 mg and meet the registration requirements; patients should be registered via FAX at the registration center until the target number of patients is registered. The patients should be registered before Day 8 of treatment counting from the initiation of treatment with Anaemetron I.V. Infusion 500 mg as Day 1.

1) Registration criteria

Patients who have not used Anaemetron I.V. Infusion 500 mg before the initiation of treatment with this drug

2) Registration items

Patient ID number, sex, age on the date of treatment initiation, date of treatment initiation with this drug, eligibility to registration criteria, and disease targeted in this study (disease for which this drug is used)

[Patient Registration Center]

[contact] (Available 24 hours a day)

(2) Exclusion from the registration

Patients found to not meet the registration criteria after the registration form is received at the registration center will be excluded from the registration.

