5.4. Subgroups

Subgroup analyses of safety will be performed for the following patient background factors.

- Presence or absence of hepatic dysfunction
- Presence or absence of renal dysfunction
- Children (<15 years), adults (≥15 to <65 years), elderly (≥65 years)
- Diagnosis* (anaerobic infection, infectious enterocolitis [incl. pseudomembranous colitis], amebic dysentery)

* The same patient may have multiple diagnoses. In such case, additional subgroups may be added (e.g., anaerobic infection plus infectious enterocolitis).

Subgroup analyses of safety will also be performed according to the following factors:

- Pregnant and parturient women (pregnancy confirmed)
- Prior treatment (medication for infection) [absent, present]
- Concomitant medications (medication for infection) [absent, present]
- Maximum number of daily doses (1, 2, 3, 4, or >4 times)
- Dose escalation [absent, present]
- Overdose ** [absent, present]

** Patients who have had a daily dose of >500 mg or had >4 doses a day are defined as having experienced overdose.

Patients in whom Anaemetro might have been contraindicated per the package insert (hereinafter referred to as contraindicated patients) will be sampled from the registry according to separately-specified criteria and be analyzed for the safety of Anaemetro as a subgroup analysis.

Subgroup analyses of effectiveness will be performed for the following patient background factors.

- Presence or absence of hepatic dysfunction
- Presence or absence of renal dysfunction
- Children (<15 years), adults (≥15 to <65 years), elderly (≥65 years)
- Diagnosis* (anaerobic infection, infectious enterocolitis [incl. pseudomembranous colitis], amebic dysentery)

* The same patient may have multiple diagnoses. In such case, additional categories may be added (e.g., anaerobic infection plus infectious enterocolitis).

Subgroup analyses of effectiveness will also be performed according to the following factors:

- Prior treatment (medication for infection) [absent, present]
- Concomitant medications (medication for infection) [absent, present]
- Maximum number of daily doses (1, 2, 3, 4, or >4 times)

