8.2.2. Patient Background and Treatment History of Anametro

- **Patient background**

In the safety analysis set, clinical response analysis set, and microbiological response analysis set, the following patient background factors will be tabulated in accordance with Section 8.1.

- Sex [male, female]
- Age (continuous)
- Age group [<15 years, ≥ 15 to <65 years, ≥ 65 years]
- Age group [≥ 10 to <20 years, ≥ 20 to <40 years, ≥ 40 to <65 years, ≥ 65 to <70 years, ≥ 70 to <75 years, ≥ 75 years]
- Inpatient/outpatient status at the first prescription [inpatient, outpatient]
- Body weight (continuous)
- Body Mass Index (continuous)
- Diagnostic name* (anaerobic infection, infectious enterocolitis, amebic dysentery, others)
- Detailed diagnosis name of anaerobic infection
- Severity [mild, moderate, severe, unknown]
- Hepatic dysfunction [absent, present]
- Renal dysfunction [absent, present]
- Past medical history other than hepatic/renal dysfunction [absent, present]
- Concurrent illness other than hepatic/renal dysfunction [absent, present]
- Prior treatment (medication for infection) [absent, present]
- Concomitant medication (medication for infection) [absent, present]

* The same patient may have multiple diagnoses. In such case, additional categories may be added (e.g., anaerobic infection plus infectious enterocolitis).

In addition, patient background will also be tabulated by maximum number of daily doses and by the presence or absence of a central nervous system disorder.

In the safety analysis set, the number and proportion of the following patients will be tabulated by SOCs and PTs of MedDRA.

- Past medical history other than hepatic/renal dysfunction

- Concurrent illness other than hepatic/renal dysfunction.

In the safety analysis set and clinical response analysis set, the number and proportion of the following patients will be tabulated.

- Presence or absence of pregnancy
- Concomitant medication (medication for infection)
- Prior treatment (medication for infection)

- **Status of treatment of Anaemetro**

In the safety analysis set, the following status of treatment of Anaemetro will be tabulated:

- Duration of treatment (continuous)
- Duration of treatment (1) [1, 2, 3, 4, 5, 6, 7, 8, 9, 10, 11, 12, 13, 14, 15, 16, 17, 18, 19, 20, 21, ≥ 22 days]
- Duration of treatment (2) [≤ 3 day, ≥ 4 to ≤ 7 days, ≥ 8 to ≤ 14 days, ≥ 15 to ≤ 21 days, ≥ 22 days]
- Duration of treatment (3) [≤ 3 days, ≥ 4 to ≤ 10 days, > 10 days]

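### SAP 5.2.1(h) and 5.2.2(j): the definition of 'non-target disease' does not match its label and can be read two ways, giving different denominators for the effectiveness rates

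*SAP*

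**What the plan says.** Protocol 7.2.1 covers patients who "have been administered this drug for treatment of anaerobic infection, infectious enterocolitis, or amebic dysentery". Protocol 7.6.2.1 asks for registration forms for patients with those three diseases and records the target disease as a registration item. The one listed registration criterion, however, is "Patients who have not used Anaemetron I.V. Infusion 500 mg before the initiation of treatment with this drug", and the registration centre excludes patients who fail the registration criteria.

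SAP 5.1 lists six exclusions from the safety set. None names the disease. The closest is criterion c, "There was a violation of registration (description in the report, “registration violation", with details left to a separate guidance.

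SAP 5.2.1(h) then excludes from the clinical response set "Non-target disease of the study (description in the report, “Non-target disease of the study", and the sentence beneath says this means that "others” is checked with no other information in the CRF item that asks the disease (diagnosis) that required the use of Anaemetro". SAP 5.2.2(j) repeats the label and the definition for the microbiological response set.

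SAP 8.2.2 tabulates "Diagnostic name* (anaerobic infection, infectious enterocolitis, amebic dysentery, others" in the safety set and both effectiveness sets. The diagnosis subgroups in SAP 5.4 are "Diagnosis* (anaerobic infection, infectious enterocolitis [incl. pseudomembranous colitis], amebic dysentery", with combinations allowed but no 'others' group. Protocol Tables 2 and 3 and SAP 6.2.1 define an effective response for the three target diseases only.

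**The concern.** The label of criteria h and j describes a patient known to have the wrong disease. The definition beneath it, on its plain wording, describes a patient whose disease was not recorded. These are different patients. Someone programming the analysis sets from the definition and someone programming them from the label could produce different sets.

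The clinical response rate is the primary effectiveness endpoint in Protocol 7.7, and Protocol 7.5.2 intends to compare effectiveness with the earlier clinical study. A retained patient with a named non-target disease would be rated without an applicable definition of response. That patient would count in the overall rate and fall in none of the diagnosis subgroups listed in SAP 5.4. The overall rate would then describe a somewhat different population from the one in Protocol 7.2.1. The eradication rate has the same problem through criterion j.

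**Working it through.** **The plan's own figure.** The only calculation in the plan that could be reproduced is the sample size: 1 − 0.97^100 = 0.952, which agrees with the stated 95% chance of seeing a 3% reaction in 100 patients. It concerns safety and does not depend on this point. The plan gives no figure for the response rate or for the number of 'others' patients.

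**The two readings applied to each kind of patient.** The literal reading is that 'others' is ticked and nothing else is entered in the diagnosis item. The alternative reading is that 'others' is ticked and no target disease is ticked.

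| Entry in the diagnosis item | Literal reading | Alternative reading |
|---|---|---|
| Target disease ticked, with or without 'others' | kept | kept |
| 'Others' only, a non-target disease written in | kept | removed |
| 'Others' only, nothing written | removed as non-target | removed as non-target |
| 'Others' only, a target disease written in | kept | removed |

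The readings disagree in the second and fourth rows. In the second row the literal reading contradicts the label. In the fourth the alternative reading would drop an eligible patient. In the third both readings call an unknown disease non-target. Rows two and four assume that the item has a free-text line; the case report form is not among the documents.

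**Whether another rule settles the second row.** Criterion c of SAP 5.1 would do so if a non-target disease counted as a registration violation. The listed registration criterion concerns prior use only, and the guidance that would decide is not available here. If criterion c already removed every such patient, h and j would have little left to do. Criteria g and i would remove the patient only if no response had been recorded. So no rule clearly settles it.

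**Size, under assumed values.** Let k of n evaluable patients have a named non-target disease. Keeping them changes the overall rate by

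(k/n) × (response rate in non-target − response rate in target).

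Take n = 100 and let the non-target response run from 0% to 100%.

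*Target response assumed to be 80%:*
- k = 5: removed, 76/95 = 80%; kept, 76/100 = 76% to 81/100 = 81% (−4 to +1 points).
- k = 10: removed, 72/90 = 80%; kept, 72/100 = 72% to 82/100 = 82% (−8 to +2 points).

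*Target response assumed to be about 85%, in whole patients:*
- k = 5: removed, 81/95 = 85.3%; kept, 81% to 86%.
- k = 10: removed, 76/90 = 84.4%; kept, 76% to 86%.
- k = 20: removed, 68/80 = 85.0%; kept, 68% to 88%.

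If k = 0 the shift is zero. The same formula applies to the eradication rate.

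**The case against.** The strongest reply is that the sentence explains its own label and should be read with it. The SAP allows several diagnoses per patient, so in a multi-tick item the wording can naturally mean that 'others' stands alone with no target disease ticked. The rule then removes named non-target patients as the label says. This reading is plausible and largely works. It would go wrong only if a site ticked 'others', left the target box blank and wrote in a target disease. Nothing in the documents shows that this happened, and Protocol 7.6.3.2 provides for queries. A reader might infer that the rule simply works backwards, or that it misclassifies patients on every reading. The documents support neither; they support an ambiguity.

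A reader might also infer that nothing upstream stops non-target patients. That goes too far. Protocol 7.2 and 7.2.1 restrict the study to the three diseases, Protocol 7.6.2.1 directs registration to them, and SAP 5.1(c) removes registration violations. Upstream control is uncertain, not absent.

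The 'others' row in SAP 8.2.2 is weak evidence that such patients remain in the effectiveness sets, because one list serves all three sets and the safety set may need that row.

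Finally, the study is not confirmatory (SAP 4.1). At 80/100 the exact 95% interval is about 71% to 87%, so a shift of −4 to +1 points lies inside it. That limits the consequence, but it does not tell a programmer which patients to exclude.

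**Conclusion.** The point stands as a defect of definition. Criteria h and j do not match their label on the literal reading, and the two available readings can give different denominators for the primary clinical response rate and for the eradication rate. Nothing else in the documents clearly decides between them.

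The size is unknown. It depends on how many patients had 'others' alone with text written in, and on their response; the documents give neither. The percentages above rest on assumed response rates of 80% and about 85%, and on 5 to 20 non-target patients per 100. They show what could happen and do not estimate what did. It would be tempting to conclude that the reported response rate is biased, but the documents do not support that, and the effect may be zero. Rates by target diagnosis are unaffected by patients classed only as 'others'. The correction is worth making because it is cheap and concerns the primary effectiveness endpoint.

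**What to change.** In SAP 5.2.1(h) and 5.2.2(j), replace the explanatory sentence with: *no target disease is ticked and, after review of the free text before database release and without reference to response, the diagnosis is none of anaerobic infection, infectious enterocolitis or amebic dysentery.* Assign free text that names a target disease to that disease. Report 'others' with no text under a separate exclusion reason, 'diagnosis unknown'.

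The cost is one sentence changed in two places, one added exclusion reason and a short review of the 'others' entries. The effectiveness sets may become slightly smaller. The timing fits, since the SAP's last log entry (August 2017) describes database release as in preparation. Changing the registration criteria is not proposed: registration was planned to end in March 2017, so a change at that stage would affect no patient.

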5.2.2. Microbiological Response Analysis Set

The microbiological response analysis set is defined as the patients in the safety analysis set excluding any patients who meet any of the following criteria:

- i. No information of microbiological response (description in the report, “no microbiological response information”)
- j. Non-target disease of the study (description in the report, “Non-target disease of the study”)

That is, “others” is checked with no other information in the CRF item that asks the disease (diagnosis) that required the use of Anaemetro.

5.3. Other Analysis Sets

Not applicable.

5.4. Subgroups

Subgroup analyses of safety will be performed for the following patient background factors.

- Presence or absence of hepatic dysfunction
- Presence or absence of renal dysfunction
- Children (<15 years), adults (≥15 to <65 years), elderly (≥65 years)
- Diagnosis* (anaerobic infection, infectious enterocolitis [incl. pseudomembranous colitis], amebic dysentery)

* The same patient may have multiple diagnoses. In such case, additional subgroups may be added (e.g., anaerobic infection plus infectious enterocolitis).

Subgroup analyses of safety will also be performed according to the following factors:

- Pregnant and parturient women (pregnancy confirmed)
- Prior treatment (medication for infection) [absent, present]
- Concomitant medications (medication for infection) [absent, present]
- Maximum number of daily doses (1, 2, 3, 4, or >4 times)
- Dose escalation [absent, present]
- Overdose ** [absent, present]

** Patients who have had a daily dose of >500 mg or had >4 doses a day are defined as having experienced overdose.

Patients in whom Anaemetro might have been contraindicated per the package insert (hereinafter referred to as contraindicated patients) will be sampled from the registry according to separately-specified criteria and be analyzed for the safety of Anaemetro as a subgroup analysis.

Subgroup analyses of effectiveness will be performed for the following patient background factors.

- Presence or absence of hepatic dysfunction
- Presence or absence of renal dysfunction
- Children (<15 years), adults (≥15 to <65 years), elderly (≥65 years)
- Diagnosis* (anaerobic infection, infectious enterocolitis [incl. pseudomembranous colitis], amebic dysentery)

* The same patient may have multiple diagnoses. In such case, additional categories may be added (e.g., anaerobic infection plus infectious enterocolitis).

Subgroup analyses of effectiveness will also be performed according to the following factors:

- Prior treatment (medication for infection) [absent, present]
- Concomitant medications (medication for infection) [absent, present]
- Maximum number of daily doses (1, 2, 3, 4, or >4 times)

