7.3.3. Concomitant therapy

7.3.3.1. Drug therapy

Medications used for the infection

The following information will be recorded for medications used for the infection during a period from 14 days before the initiation of treatment with this drug to the completion date of observation period.

- [1] Drug name (product name)
- [2] Route of administration
- [3] Date of treatment initiation
- [4] Presence/absence of concomitant use at the time the treatment with this drug begins

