7.5. Study size

7.5.1. Planned sample size

100 patients (for safety analysis)

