7.5.2. Rationale for sample size

The target sample size was set to be 100 patients, which should enable to detect, at 95% probability, an adverse reaction of which the true incidence rate is 3% in reference to adverse reaction of the least incidence in a clinical study of this drug (Study A6831005). This sample size should enable to confirm whether the types and incidence of adverse reaction related to this

drug used for diseases other than intra-abdominal infection, and pelvic inflammatory disease and other related diseases (hereinafter referred to as "PID") that were targeted in the clinical study would be similar to those occurred in Study A6831005.

Events specified as important identified risks or important potential risks in the Risk Management Plan (RMP) may not have a high incidence, and thus, may not detect sufficient information only from the drug use investigation; nonetheless, such an event collected in the drug use investigation should be investigated within the framework of the drug use investigation. Moreover, these events should also be monitored through the routine pharmacovigilance activities.

The sample size of 100 patients are expected to enable accumulating data on the number of patients at the level similar to the clinical study in terms of clinical response rate of this drug for diseases other than intra-abdominal infection and PID that were targeted in the clinical study and also in terms of clinical response rate in subgroup analysis by each major indication; which should enable verification whether the effectiveness under actual clinical settings is similar to the results of the clinical study.

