8.2.3.4. Subgroup Analysis

The number and proportion of patients who experienced at least one adverse reaction will be tabulated for each factor specified in Section 5.4. To evaluate the relationship between patient background factors and the development of adverse reactions, the analysis based on risk ratio and risk difference specified in Section 8.1.3 will be performed. For subgroups with

risk ratio ≥ 2 or ≤ 0.5 , the number and proportion of patients who experienced adverse reaction will be summarized for each factors, using SOCs and PTs. It should be noted that if adverse reactions developed in less than a total of 10 patients, the risk ratio and risk difference will not be calculated, although the proportion will be presented for each factors.

The number and proportion of patients who experienced adverse reaction will be summarized by maximum number of daily doses, based on SOCs and PTs. Similarly, the number and proportion of patients who experienced serious adverse reaction will be summarized by maximum number of daily doses.

Listing of adverse reactions that developed in contraindicated patients will be tabulated. In addition, the number and proportion of those contraindicated patients who experienced adverse reactions will be tabulated by SOC and PT, as necessary.

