8.2.4. Effectiveness Analysis

8.2.4.1. Clinical Response

In the clinical response analysis set, the number and proportion of patients with each clinical response will be calculated. In addition, the number and proportion (response rate) of responders and the 95% CI of response rate will be calculated in the clinical efficacy analysis set excluding patients with indeterminate response. Similar calculations will be tabulated by diagnosis (including by detailed diagnostic name of anaerobic infection), by maximum number of daily doses, and by the occurrence of central nervous system disorder. The response rate can be calculated by the following formula:

Clinical response rate (%) = (Number of patients with “effective”/ Number of clinically-evaluable patients excluding “indeterminate”) $\times 100$.

If the clinical efficacy analysis set includes patients with inconsistent clinical efficacies, the response rate will be calculated by subtracting those patients from the denominator, as in the case where the set includes “indeterminate” patients.

In addition, the number and proportion (clinical response rate) of responders and the 95% CI of response rate for each pathogenic organism/strain will also be tabulated by diagnosis.

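### Maximum daily doses, dose escalation and overdose are known only after the treatment course, so their crude risk ratios can depart from 1 when the factor has no effect

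*SAP*

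**What the plan says.** **Factors.** SAP 5.4 has a list of patient background factors and, for safety and again for effectiveness, a second list. The second safety list includes "Maximum number of daily doses (1, 2, 3, 4, or >4 times"), "Dose escalation [absent, present"], overdose (defined as ever having exceeded a stated limit) and "Concomitant medications (medication for infection) [absent, present"]. The second effectiveness list repeats maximum daily doses and concomitant medications.

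**Comparison.** SAP 8.2.3.4 tabulates reactions for each section 5.4 factor and applies the risk ratio and risk difference of SAP 8.1.3, to relate background factors to reactions. A risk ratio of at least 2 or at most 0.5 triggers a breakdown by SOC and PT. No ratio is calculated if fewer than 10 patients have a reaction. SAP 8.2.4.4 applies the same measures to clinical and microbiological response, with no such minimum. Appendix 2 sets 1, 2, 4 and more than 4 daily doses each against 3, and also lists dose escalation.

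**Descriptive tables.** Separately, reactions "will be summarized by maximum number of daily doses, based on SOCs and PTs" (SAP 8.2.3.4), and response rates are given "by maximum number of daily doses, and by the occurrence of central nervous system disorder" (SAP 8.2.4.1).

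**Time window.** Observation runs from the start to the end of treatment, cut off at Day 56 (Protocol 7.2.6), and the safety analysis rests primarily on that window (SAP 8.2.3). An adverse event is a listed reason for discontinuation (Protocol 7.3.5).

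**Concomitant drugs.** Protocol 7.3.3.1 collects anti-infectives from 14 days before treatment to the end of observation. Its item [4] is "Presence/absence of concomitant use at the time the treatment with this drug begins". Table 1 marks the item at initiation of treatment.

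**The concern.** A risk ratio between subgroups is easy to read only if the grouping is settled before the outcome can occur. Here it is not, and three mechanisms follow.

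- A reaction that stops treatment also stops any later escalation. Reactors are then over-represented among those who never escalated or who stayed at a low maximum frequency.
- A longer course gives more time both to escalate and to react, which pushes the ratio the other way.
- An escalation after a reaction counts as exposure, although it cannot have caused that reaction.

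The plan has no landmark, no rule that exposure must precede the event, no person-time analysis and no adjustment for duration. SAP 6.4 names no covariates. At stake are the planned analyses of factors affecting reactions and response, which feed the re-examination application (SAP 3). For dose escalation and overdose, the ratio also decides whether an SOC/PT breakdown is made.

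**Working it through.** **The plan's own figure.** For 100 patients and a 3% true incidence, the probability of at least one case is 1 − 0.97^100 = 0.952. The smallest sufficient n is ln 0.05 / ln 0.97 = 98.4, so 99. The 100 in Protocol 7.5 reproduces and is not affected by this point. The documents state no figure for the subgroup ratios.

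**Inputs for the null check (assumed, not in the documents).** Escalation hazard e = 0.03 per day; reaction hazard r = 0.015 per day, the same before and after escalation. The true ratio is therefore 1.

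**(a) Fixed 14-day course, no reaction stops treatment.** Escalation and reaction are independent. The reaction risk is 1 − exp(−0.21) = 0.189 in both groups, so RR = 1.00.

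**(b) Fixed 14-day course, every reaction stops treatment.**
- P(escalated) = e/(e+r) × [1 − exp(−0.63)] = 0.667 × 0.467 = 0.312
- P(escalated, no reaction) = exp(−0.21) × [1 − exp(−0.42)] = 0.811 × 0.343 = 0.278
- P(escalated and reaction) = 0.312 − 0.278 = 0.034
- P(reaction, not escalated) = 0.189 − 0.034 = 0.156 (unrounded inputs)
- Risks: 0.0336/0.3116 = 0.108 against 0.1558/0.6884 = 0.226, so RR = 0.48

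**(c) Half the patients on 7 days, half on 14, no stopping.**
- P(escalated) = (0.189 + 0.343)/2 = 0.266
- P(reaction) = (0.100 + 0.189)/2 = 0.145
- P(both) = (0.189 × 0.100 + 0.343 × 0.189)/2 = 0.042
- Risks: 0.0419/0.2662 = 0.157 against (0.1445 − 0.0419)/0.7338 = 0.140, so RR = 1.13. A wider spread of durations raises it.

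**Simulated ranges under the null** (assumed: reaction risk 10–30%; 10–30% of patients escalate; for 1 v 3 doses, 5–10% truly once daily and a partial first day):

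| Contrast | Every reaction stops | Half stop | None stop |
|---|---|---|---|
| Escalation, fixed 7 or 14 days | 0.46–0.55 | 0.71–0.79 | about 1.00 |
| Escalation, mixed 3–21 days | 0.69–0.74 | 1.06–1.09 | 1.37–1.48 |
| Maximum doses, 1 v 3 | 1.32–1.70 | 1.15–1.33 | about 1.00 |
| Maximum doses, 2 v 3 | 1.18–1.23 | 1.08–1.11 | about 1.00 |

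In the same runs, classing by the prescribed starting regimen gave 0.98–1.01 and a person-day rate ratio for escalation gave 0.96–1.04. A Day 3 landmark gave 0.87–1.05, mostly 0.95–1.05.

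**The 0.5 cut-off at N = 100.** With a 14-day course, every reaction stopping treatment and a 15–20% reaction risk, 53–56% of null data sets give an escalation RR of 0.5 or less. A baseline factor of equal size does so in 12–33%. The 10-patient minimum is met in 95–100% of these data sets.

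**Concomitant drug, only if it means any time.** Assume 80% response, 30% on a drug at the start, and a drug added later in 10% of the remaining responders and 50% of the remaining non-responders.
- Present: 0.30 + 0.70 × (0.8 × 0.1 + 0.2 × 0.5) = 0.426
- Responders among present: 0.8 × (0.30 + 0.07) = 0.296, a rate of 69%
- Absent: (0.8 − 0.296)/0.574 = 88%, so RR = 0.79

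With 70–90% response and additions in 30–50% of non-responders, the range is 0.71–0.94. It is 1.00 if additions do not depend on response, or if status at the start is used.

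**The case against.** The case for leaving the plan alone has several sound parts.

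- **A reader might infer that these ratios are always biased.** The documents do not support that. Bias needs outcome-dependent stopping or dosing, or courses of differing length. Case (a) gives exactly 1.00, and with half of reactions stopping treatment in mixed courses the ratio is only 1.06–1.09.
- **A reader might infer that concomitant use is counted at any time.** The SAP does not say so. Table 1 and item [4] point to the start of treatment, while the collection window runs to the end of observation. What is established is a missing time point.
- **A reader might infer that the 2 and 0.5 cut-offs act on a biased dose-frequency ratio.** They have little to act on there: the SOC/PT table by maximum daily doses is made whatever the ratio, and effectiveness has no cut-off.
- **The tables quoted from 8.2.3.4 and 8.2.4.1 are proportions, not ratios.** As description they are unobjectionable.
- **The SAP calls its tests exploratory (4.1) and has no decision rules (4.2).** Protocol 7.9 already warns about confounding.

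All of this stands and lowers the severity. It does not remove the point. An exploratory label does not correct a systematic error, the 10-patient minimum is met in most of the scenarios that matter, and a general caution about confounding does not tell a reader that the grouping itself depends on the outcome.

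**Conclusion.** The point holds for maximum number of daily doses, dose escalation and overdose. They are defined over the course but compared by crude ratio as if they were background factors. Under the assumed hazards the null escalation ratio lies between about 0.5 and about 1.4, and is about 1.0 for a fixed course without stopping. The documents give no reaction, escalation or stopping rates, so neither the size nor the direction in this study can be stated. Overdose was not simulated separately; it has the same structure where the limit is first exceeded after treatment starts. For concomitant medication the finding is an undefined time point, with the same bias only under an any-time reading. Severity is modest: the SAP should be changed, but no confirmatory conclusion depends on it.

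**What to change.** In SAP 5.4, 8.2.3.4, 8.2.4.4 and Appendix 2:

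1. For risk ratios and risk differences, class dose frequency by the starting regimen. Use the regimen rather than the count on Day 1, because a partial first day can understate it.
2. Define concomitant anti-infective use by item [4] of Protocol 7.3.3.1.
3. For reactions by dose escalation or overdose, use a person-day rate ratio with exposure as time-dependent, or a landmark. Otherwise tabulate without a risk ratio.
4. Do not use a crude risk ratio that counts only dosing before the first reaction. It shortens the exposure window in reactors alone. In case (a) it would reproduce the classification of case (b) and turn a correct 1.00 into 0.48.
5. Keep the tables by maximum number of daily doses, labelled as description.

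The cost is SAP wording and some re-derivation from the dosing record (Protocol 7.3.2), reaction onset dates (7.3.7) and item [4]. Step 3 needs each dosing regimen to carry its own dates. The protocol does not say so outright, although the SAP's mean number of daily doses and its exclusion of suspended days suggest it. The downside is fewer patients in the higher-frequency groups.
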